4. TYPE OF STUDY

A phase IV study of low level of intervention, open, prospective, randomized and controlled is proposed that aims to compare the analgesic efficacy of the proposed locoregional anesthetic techniques (PENG AND BNFCL) with two of the most frequently used local anesthetics in patients with hip fracture (Levobupivacaine and Ropivacaine) to whom surgical osteosynthesis (endomedullary interlocking or hip hemiarthroplasty) will be performed. The study begins in the preoperative period, applying an anesthetic protocol in the operating room and then followed up for at least 48 hours in the postoperative period.

The necessary sample size will be 108 patients, 54 patients per branch (Ropivacaine and Levobupivacaine). This figure could be increased to X patients in case of 10% losses due to complications during surgery.

5. JUSTIFICATION OF LOW LEVEL OF INTERVENTION

The medicines (Levobupivacaine and Ropivacaine) studied in this project are used in accordance with the authorised SmPC.

In the present trial, no additional procedures are performed with respect to those that would have been performed on participants in the context of routine clinical practice, both in Spain and in the European Union and other international settings.

6. MATERIAL AND METHODS

6.1. SCOPE OF STUDY

Unicentric study, which will be carried out in the Anesthesiology and Resuscitation Service of the CAUSA.

6.2. STUDY PERIOD AND RECRUITMENT PLAN

Start in October 2020 until the number of patients is completed. A rate of 15 patients/month is calculated, which means an expected completion in April 2021.

Patients will be selected from among the elderly with hip fracture who come to causa. Patients will be provided with detailed informed consent in plain language for review and given sufficient time to answer all questions related to the study. After signing the consent, it will be checked if they are eligible for the study according to the inclusion and exclusion criteria.

6.3. INCLUSION CRITERIA

- The patient will have to voluntarily sign and understand the informed consent that will be provided to him in writing.
- Patients over 65 years of age, with hip fracture, who are going to be operated on at the University Care Complex of Salamanca (CAUSA).

6.4. EXCLUSION CRITERIA

Patients who meet any of the following exclusion criteria will not be eligible to participate in this study:

- Rejection of the technique.
- Allergy to any of the drugs. Coagulation
- disorders. Local infections instead of
- puncture. Vascular prostheses at the
- femoral level.

6.5. RANDOMIZATION PROCESS

Randomization will be performed by means of a computer program (SPSS[®] v. 25.0) that generates two treatment groups and randomly assigns the selected patients to each of the groups in a simple random way (1:1).

6.6 . WITHDRAWAL CRITERIA FOR STUDY SUBJECTS

Patients will be removed from the trial when they meet any of the following criteria:

- Withdrawal of consent
- Complications during surgery that in the opinion of the researcher invalidate the results of the study
- Lack of collaboration or inability to evaluate the pain scales used in the study.

Patients who leave the trial for any reason may not be re-included. At the time of leaving the trial, the main reason for withdrawal of the trial must be recorded. The data collected up to the time of withdrawal may be included for analysis of results.

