1.12. STUDY DESIGN

Prospective clinical trial (phase IV) of low level of non-commercial intervention, comparative of balanced, randomized groups, to compare the analgesic efficacy of the local anesthetics Ropivacaine and Levobupivacaine in peripheral nerve block in hip fracture surgery of the elderly.

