1.15. STUDY POPULATION AND TOTAL NUMBER OF PATIENTS

Patients over or equal to 65 years of age who are going to undergo hip surgery for fracture.

The necessary sample size will be 108 patients, 54 patients per branch (Ropivacaine and Levobupivacaine), assuming 10% of losses.

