6.9. JUSTIFICATION OF SAMPLE SIZE

Taking into account the Pharmacokinetics of both local anesthetics, and previous studies(28, 29), using the G*Power program, the sample size is calculated. We consider significant a difference in the duration of the blockade of at least 3 h, with a deviation of 50%. The security level or alpha error is 5%. The beta error is 20%. A total of 108 patients were obtained, 54 in each of the lines of intervention, assuming 10% of losses.

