6.11. ASSESSMENT OF EFFICACY

The main endpoint of the study's effectiveness will be the difference in the duration of the blockade.

6.12. POLICY REGARDING INTERMEDIATE ANALYSES AND CRITERIA FOR EARLY COMPLETION OF THE TRIAL.

This clinical trial may be stopped earlier than expected by the result of an interim analysis demonstrating greater than expected benefit or harm in any of the treatment arms. 1 formal internal efficacy and safety analysis will be carried out when 50% of the expected number of participants are reached. Poor study performance (e.g., slow patient recruitment, high rates of follow-up losses, or poor quality control) may be another cause of early study discontinuation.

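### Simple 1:1 randomisation does not guarantee the balanced groups of 54 and leaves surgery type to chance; stratified blocks and a prespecified surgery-type term are a cheap improvement

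*Combined protocol and SAP*

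**What the plan says.** - **Allocation.** Section 6.5 states that SPSS generates two treatment groups and "randomly assigns the selected patients to each of the groups in a simple random way (1:1"). It mentions no blocks, strata or minimisation. It does not say who holds the list or when an allocation is released.
- **Balance.** Section 1.12 describes the trial as "comparative of balanced, randomized groups". Section 1.15 states "The necessary sample size will be 108 patients, 54 patients per branch (Ropivacaine and Levobupivacaine), assuming 10% of losses", and section 6.9 repeats 54 in each arm.
- **Surgery type.** Section 1.13 admits both partial prostheses and intramedullary nailing. Section 6.7 and Annex III record the type, with a third category for others. It is not a stratification factor.
- **Analysis.** Section 6.10 compares the groups by Student's t or Mann-Whitney according to normality tests. It then promises multiple linear regression for confounders, without naming a covariate.
- **Interim look.** Under section 6.12 one formal analysis "will be carried out when 50% of the expected number of participants are reached", and the trial may stop on its result.
- **Setting.** Section 4 calls the study open; section 6.1 makes it single-centre.

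**The concern.** The design summary describes a property, balanced groups, that the stated allocation method does not secure. With about 100 patients, unrestricted allocation often gives visibly unequal arms, and nothing ties the mix of operations in one arm to the mix in the other. Hemiarthroplasty and nailing are different operations and could plausibly differ in postoperative pain, and so in how long analgesia appears to last. An uneven mix would then add noise to the estimated difference in block duration and invite doubt about a positive result. The effect is stronger at the half-way analysis, where the sample is half as large and stopping is possible. Regression is promised, but because no covariate is named, adjustment for surgery type could be included or omitted after the data are seen.

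**Working it through.** **The plan's own figure.** The 54 per arm cannot be reproduced with certainty. Section 6.9 says "We consider significant a difference in the duration of the blockade of at least 3 h, with a deviation of 50"%, with no base for the percentage, and does not say whether the test is one- or two-sided. Reading it as a standardised difference of 0.5 (SD 6 h, an assumption) with alpha 5% and power 80% gives 50 to 51 per arm one-sided and 63 to 64 two-sided for a t test before losses. The balance calculations below need only the total of 108. Whether losses are inside that total (sections 1.15 and 6.9) or on top of it (section 4: "This figure could be increased to X patients in case of 10% losses due to complications during surgery") is a separate inconsistency.

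**1. Arm sizes.** Under simple 1:1 allocation the size of one arm is X ~ Binomial(108, 0.5), with SD √(108 × 0.25) = 5.2.
- P(54/54) = C(108, 54) / 2^108 = 7.7%.
- Central 95% range: 44 to 64 per arm.
- P(arms differ by 10 or more) = 2 × P(X ≥ 59) = 38.7%.
- P(arms differ by 20 or more) = 2 × P(X ≥ 64) = 6.7%.
- Interim, 50% of 108 = 54 patients, X ~ Binomial(54, 0.5): P(arms differ by 10 or more) = 2 × P(X ≥ 32) = 22.0%.

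**2. What unequal arms cost.** Relative efficiency is 4·n1·n2 / 108². For 48/60 it is 4 × 48 × 60 / 11,664 = 0.988; for 44/64 it is 4 × 44 × 64 / 11,664 = 0.966. Power comes from the noncentral t distribution with noncentrality 0.5 × √(n1·n2 / 108), using the assumed difference of 0.5 and no losses:

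| Split | Noncentrality | Power, one-sided | Power, two-sided |
|---|---|---|---|
| 54/54 | 2.598 | 82.6% | 73.1% |
| 48/60 | 2.582 | 82.1% | 72.5% |
| 44/64 | 2.553 | 81.4% | 71.6% |

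The loss at 44/64 is 1.2 points one-sided and 1.5 two-sided. Averaged over all splits it is 0.3 to 0.4 points.

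**3. Surgery type.** The documents give no expected shares, so I take p = 30% to 50% in the less common type. The between-arm difference in that share has standard error approximately √(4·p·(1 − p) / N).

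| N | p | SE | P(gap ≥ 15 points) |
|---|---|---|---|
| 108 | 0.3 | 0.088 | 9% |
| 108 | 0.4 | 0.094 | 11% |
| 108 | 0.5 | 0.096 | 12% |
| 54 | 0.3 | 0.125 | 23% |
| 54 | 0.4 | 0.133 | 26% |
| 54 | 0.5 | 0.136 | 27% |

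Simulating simple allocation gives the same ranges. At N = 108 a gap of 10 points or more has a chance of 27% to 31%.

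**4. With the change.** In permuted blocks of maximum size b, a stratum can be out of balance by at most b/2. Two strata with b = 4 (an illustration) hold the arms within 2 + 2 = 4 patients, 52/56 at worst. With 54 patients in each stratum, the worst surgery split is 28/54 against 26/54, a gap of 3.7 points.

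**The case against.** The best defence is that little is at stake. In section 1.12, balanced may mean only a 1:1 ratio, and 54 per arm is a sample-size target, not a promise of an exact split. In a translated text, generating two groups might even describe a fixed-size split. Unequal arms cost almost nothing in power, and section 6.12 does not require equal arms at the interim. Imbalance that arises by chance under valid randomisation is already covered by the test's error rate, and section 6.10 plans regression. Simple randomisation is also the least predictable scheme, so blocks in an open single-centre trial give something up. All of this stands, and it limits the point to a cheap improvement. What remains is that nothing protects the balance of surgery type and that the adjustment is left undefined.

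Four stronger readings are tempting, and the documents support none of them.
- **That 54/54 is unattainable.** It has a 7.7% chance; the method merely does not guarantee it.
- **That surgery type will be unbalanced.** Balance is left to chance, and a gap under 15 points is the likelier outcome even at the interim.
- **That imbalance shifts the result by a given number of hours.** The documents give no block duration by type of surgery, so no shift can be calculated.
- **That enrolling staff can see the list.** Open in section 4 means unmasked. Section 6.5 is silent on who holds the list, which is missing detail, not evidence that it is exposed. Section 6.2 does place the eligibility check after consent, but does not link it to release of the allocation.

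**Conclusion.** The point holds as a worthwhile, low-cost improvement. Simple randomisation of 108 patients does not guarantee the groups of 54 that the plan describes, although the resulting power loss is about 1 to 1.5 points even at 44/64. The better reason for change is surgery type: the final chance of a gap of 15 points or more is about one in ten, and at the interim look about one in four. This is a matter of precision and credibility, not of bias or validity.

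The arm-size probabilities rest only on the stated total and method, read as unrestricted allocation. The power figures assume a standardised difference of 0.5 and no losses. The surgery-type figures assume that 30% to 50% of patients have the less common type. How far surgery type predicts block duration is not known from the documents, so the gain in precision cannot be put in hours.

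**What to change.** - **Section 6.5.** Replace simple randomisation with permuted blocks of randomly varying, undisclosed sizes, stratified by planned surgery (hemiarthroplasty versus nailing or other). State who generates and holds the list, and that each allocation is released only after consent and eligibility are recorded. Record planned surgery at that moment.
- **Section 6.10.** Make the primary comparison of block duration a linear model with treatment and surgery type as prespecified terms, or a van Elteren rank test stratified by surgery type if the data are non-normal, with the rule for choosing written down beforehand. This replaces the unadjusted t or Mann-Whitney test followed by regression on unnamed covariates.
- **Section 1.12.** Say whether balanced means the 1:1 ratio or equal numbers.

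The cost is a rewritten paragraph in each of two sections, a new list, and someone to hold it; there are no extra patients or measurements. The downside is that blocks are slightly predictable in an open single-centre trial, which varying and undisclosed sizes limit. If that is unacceptable, keep simple randomisation and adopt only the prespecified adjustment for surgery type.

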1.16. DURATION OF PROCESSING

The duration of the treatment of each patient will be considered until the evaluation of the analgesic scale corresponding to the 48 h of the performance of the procedure. Patients may also be discontinued from the study at the discretion of the investigator at an earlier time or if they withdraw their consent at any time.

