6.10. STATISTICAL ANALYSIS

A descriptive analysis of the variables collected will be carried out. Non-categorical ones shall be expressed as median +/- IQR (interquartile amplitude). Categorical variables shall be expressed as percentages or frequencies.

After performing the relevant normality tests (Kolmogorov-Smirnov or Shapiro-Wilk), the sample differences will be determined by t-Student or Mann-Whitney U tests. In the comparison of pain scales we will use the analysis of variance (ANOVA or Kruskal-Wallis).

The comparative analysis of the categorical variables will be carried out by means of Chi-square tests with cross tables.

The control of the possible intermediate and confusing variables will be carried out by means of Multiple Linear Regression Analysis.

The significance level will be, by default, 5% (p<0.05).

All calculations will be carried out with the statistical program SPSS[®] 25.0 for Mac.

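### Section 6.6 removes randomised patients on the researcher's opinion after the study block, and no analysis population or rule for an unobserved end of block is stated

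*Combined protocol and SAP*

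**What the plan says.** Section 6.6 lists three grounds on which a patient is taken out of the trial: withdrawal of consent; "Complications during surgery that in the opinion of the researcher invalidate the results of the study"; and "Lack of collaboration or inability to evaluate the pain scales used in the study". The wording is mandatory. Section 1.16 adds a further route: "Patients may also be discontinued from the study at the discretion of the investigator at an earlier time".

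On the records of removed patients, section 6.6 says two things: "At the time of leaving the trial, the main reason for withdrawal of the trial must be recorded" and "The data collected up to the time of withdrawal may be included for analysis of results".

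Section 4 describes the design: "A phase IV study of low level of intervention, open, prospective, randomized and controlled is proposed". Section 6.11 makes the difference in block duration the main endpoint. For its comparison section 6.10 says that "the sample differences will be determined by t-Student or Mann-Whitney U tests". Neither section names an analysis population, a rule for a patient whose block end was not observed, or a sensitivity analysis. Section 10 gives the analysis to the research team.

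**The concern.** The treatment is a single injection. Once it has been given, taking a patient out of the trial cannot change exposure; it can only lose the outcome. Whether a surgical complication invalidates the results is left to a researcher who may know the arm. If such judgements are related to duration and differ between arms, the groups compared are no longer the randomised ones.

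The analysis side is also open. A t or Mann-Whitney test needs a completed duration, which a patient removed during surgery will usually lack. The text permits use of partial data without requiring it and gives no method. The team could therefore drop these patients, or count their time to withdrawal as duration, and decide after seeing the results. At stake are the type I error of the primary comparison, a possible shift in the estimate, and some power.

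**Working it through.** **1. When each criterion can act.** Section 6.8 and Annex I put the PENG and lateral femoral cutaneous blocks before the spinal and surgery. The surgical-complication criterion therefore acts only after the study dose. Section 6.7 scores the scales from arrival in the operating room, so the scale criterion can act before or after the block. So can the discretion in 1.16.

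**2. The plan's sample size.** Section 6.9 states: "A total of 108 patients were obtained, 54 in each of the lines of intervention, assuming 10% of losses". Its inputs are a 3 h difference, a deviation of 50%, alpha 5% and beta 20%. The base of the 50% is not given, so 108 cannot be reproduced directly. Read as 50% of 3 h (SD 1.5 h), the formula gives 4 per arm. Working backwards:

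- 54 × 0.9 = 48.6, so 49 evaluable and 5 lost per arm.
- Two-sided 5%, 80% power: d = (1.96 + 0.842) × √(2/49) = 0.566, or 0.572 with the t distribution.
- SD = 3 / 0.572 = 5.25 h. This is an assumption. The range used is 1.5 h to 6.2 h (one-sided test, 54 per arm, d = 0.482).

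**3. How many might be removed.** No complication rate is given. Sections 1.15 and 6.9 treat 10% as a general allowance for losses; section 4 ties it to surgical complications. Five per arm is an illustration, not an estimate.

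**4. Power for a true 3 h difference, SD 5.25 h.** The noncentrality is (3/5.25) / √(2/n).

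- n = 49: 0.571 / 0.202 = 2.83, power 80%.
- n = 54: 0.571 / 0.192 = 2.97, power 84%.

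**5. Type I error when removed patients are excluded.** Simulation of 40,000 null trials, 54 per arm, t test. In each arm the k patients most extreme on a removal score are dropped; the score has the stated correlation with duration.

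| Removed per arm | No selection, or equal in both arms (correlation 0 to 0.5) | One arm only (0.3; 0.5) |
|---|---|---|
| 1 | 4.8–5.1% | 4.8%; 5.3% |
| 2 | 5.0–5.3% | 5.2%; 5.7% |
| 3 | 4.9–5.4% | 5.4%; 6.1% |
| 5 | 4.9–5.6% | 5.9%; 7.3% |

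Repeat runs of the last one-arm cells gave up to 7.6%. The one-arm shift with 5 removed is 0.052 and 0.087 SD, that is 0.052 × 5.25 = 0.27 h and 0.087 × 5.25 = 0.46 h. At SD 1.5 h it is about 0.1 h; at 6.2 h, 0.3 to 0.5 h.

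Check by formula: type I error = 1 − Φ(1.96 − δ/SE) + Φ(−1.96 − δ/SE), with SE = √(2/49) = 0.202 SD.

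- δ = 0.052: δ/SE = 0.257, giving 0.044 + 0.013 = 5.8%.
- δ = 0.087: δ/SE = 0.431, giving 0.063 + 0.008 = 7.1%.

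**6. Type I error when the handling is chosen late.** Simulation of 40,000 null trials with gamma durations (mean 10.5 h, SD 5.25 h), withdrawal at 2 to 6 h (all assumed) and the same removal rule in both arms. The smaller p-value is taken from excluding removed patients or counting time to withdrawal as duration.

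| Removed in total | Type I error |
|---|---|
| 2 | 5.8–6.0% |
| 4 | 6.0–6.2% |
| 6 | 6.3–6.4% |
| 10 | 6.6–6.7% |

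Other runs of a late choice gave about 5.5 to 6.4%. Either rule fixed beforehand gives 4.7 to 5.2%. With 10 removed, a split of 7:3 or wider between arms arises by chance in about 32% of trials.

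**The case against.** The strongest reply is that the documents show no bias. They give no mechanism for selection in one arm, and without it the error is close to nominal. The 5.6% at the top of the equal-selection range partly reflects removing exactly five per arm by ranking; with patient-by-patient removal at the same expected rate it was 5.0%. The late-choice figures need an analyst to run both handlings and keep the better, which no section proposes. All of this stands, and it limits the point to a modest, assumption-dependent risk.

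Four stronger readings are tempting, and the text does not support them:

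- *Every removal falls after the block.* This is certain only for surgical complications.
- *Patients who cannot self-report are removed.* The criterion concerns the scales used in the study, and PAINAD is scored by observing behaviour.
- *Patients can vanish unrecorded.* Section 6.6 requires the main reason to be recorded. That limits silent removal but does not settle who is analysed.
- *The loss was unforeseen.* Section 4 expects it. An allowance for losses protects power, however, not the comparability of the arms.

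It can also be said that a censoring-based test is no cure. In 8,000 null trials with 5 per arm lost at random, a restricted mean comparison had type I error 5.8%, against 5.4% for removal plus t test; power was 81% against 80%. That stands: the gain comes from continued follow-up and a fixed rule, not from the choice of test.

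**Conclusion.** The point holds as a gap in the plan. Followed as written, section 6.6 produces discretionary post-randomisation exclusions after the only study dose in an open trial, and nothing in 6.10 or 6.11 fixes who is analysed or how an unobserved end of block is treated. It should be corrected.

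The true size cannot be derived from the documents. The figures above rest on an SD that is back-solved rather than stated, on 5 removals per arm as an illustration, and, for the higher error rates, on assumed one-arm selection or an assumed late choice. They show a modest inflation and a loss of about four points of power. They do not show that the result will be biased, or in which direction.

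**What to change.** - **Sections 6.6 and 1.16:** limit removal from data collection to withdrawal of consent. Patients with surgical complications then stay in the planned follow-up to end of block or 48 h. This concerns data only and changes no clinical care.
- **Section 6.10, population:** state that the primary analysis includes all randomised patients in their assigned arm.
- **Section 6.10, unobserved end of block:** pre-specify one rule, for example censoring at the last assessment with a comparison that can handle censoring. The choice of test is the sponsor's. If no scale can be evaluated, say in advance whether the recorded time to rescue is used or the duration is treated as unobserved under the same rule.
- **Data up to withdrawal:** replace the permission with a definite statement of whether they are used.
- **Researcher-judged exclusions:** keep them for a sensitivity analysis, decided without knowledge of arm or duration, with numbers and reasons reported by arm.

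**Cost:** an amendment, and a few entries added to the Annex III form, which lists no end-of-block time, last-contact time or withdrawal reason. No new visit is needed: end-of-effect scoring (section 6.7) and 48 h follow-up (Annex II) are already planned. Retained patients add some noise, not quantified here. Censoring assumes that loss is unrelated to duration. If 5 per arm were still lost at 2 to 6 h under one-arm selection (correlation 0.3 to 0.5), a restricted mean would still shift by 0.19 to 0.26 h, against 0.27 to 0.41 h with removal.
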